Absolute and percentage change in SCORAD Index from Baseline to Day 169 (Week 24) and over time. Absolute and Percentage change in affected BSA from Baseline to Day 169 (Week 24) and over time. Absolute and Percentage change in POEM from Baseline to Day 169 (Week 24) and over time. • Absolute and Percentage change in DLQI from Baseline to Day 169 (Week 24) and over time. Absolute and Percentage change in ADCT from Baseline to Day 169 (Week 24) and over time. Absolute and Percentage change in HADS from Baseline to Day 169 (Week 24) and over time. • Absolute and Percentage change in weekly average of pruritus NRS from Baseline to Day 169 (Week 24) and over time. • Proportion of patients with improvement (reduction) of weekly average of pruritus NRS ≥3 with a Baseline pruritis NRS of ≥3 from Baseline to Days 113 (Week 16) and 169 (Week 24). PD endpoints: Anti-KY1005 antibody titre and number of patients with positive response. Main exploratory endpoints: **Statistical analysis:** Sample Size: A sample size of 350 patients (70 patients / treatment arm) in the target population, (adults with moderate-to-severe AD who have a documented history, within 6 months prior to Baseline, of either inadequate response to topical treatments or inadvisability of topical treatments), randomised 1:1:1:1:1 to 4 KY1005 groups or Placebo group is estimated to provide at least 84% power to detect a pairwise difference in means between each KY1005 and Placebo with respect to the percentage change in EASI from Baseline to Day 113 (Week 16), based on a 2-sided 2-sample equal-variance t-test. **Analysis Sets:** Efficacy Analysis Set: The full analysis set (FAS) includes all randomised patients. Efficacy analysis will be based on treatment allocated at randomisation and stratified by disease severity (moderate/severe) and region. Methods: Statistical analysis of all endpoints will be defined in detail in the Statistical Analysis Plan. For continuous variables, descriptive statistics will include: the number of patients, mean, median, standard deviation, minimum, and maximum. For categorical or ordinal data, frequencies and percentages will be displayed for each category.

1-Mar-2022

Efficacy Analyses:

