An overall test for the treatment effect of KY1005 will be conducted. For each treatment regimen and all efficacy variables, the analysis will be comparisons of each of the KY1005 treatment groups with the Placebo group. For the primary endpoint, the overall type I error rate will be controlled using a hierarchical testing procedure across the four dose regimens against placebo. For each secondary endpoint analyzed, the same multiplicity adjustment approach will be applied as for the primary endpoint. No multiplicity adjustment will be made across the endpoints.

1-Mar-2022

Version number: 1

For the continuous endpoints: An analysis of covariance (ANCOVA) model will be used. This model includes treatment, randomisation strata (region, disease severity) as fixed effects, and baseline value as a covariate.

A mixed-effect model with repeated measures will be used as a sensitivity analysis for primary and continuous key secondary endpoints. This model includes the factors (fixed effects) for treatment, randomisation strata (region, disease severity), visit, treatment-by-visit interaction, and relevant baseline value.

For the categorical endpoints: Cochran-Mantel-Haenszel test stratified by randomisation strata (region, disease severity) will be used at each analysis timepoint.

Data will be presented graphically, where applicable, and with summary statistics by visit and by treatment regimen.

Safety Analyses:

Adverse events will be coded using the Medical Dictionary for Regulatory Activities (MedDRA, latest version) and will be summarised in incidence tables by System Organ Class and Preferred Term, and by treatment regimen. Adverse events will be further summarised by maximum severity and relationship to study medication. Concomitant medications will be coded using the World Health Organization Drug Dictionary and will be summarised in incidence tables by Drug Class and Preferred name, and by treatment regimen.

Other routine safety assessments such as vital signs, 12-lead ECG and safety laboratory tests will be summarised by treatment regimen using statistics for continuous or categorical data, as appropriate.

Pharmacokinetic Analyses:

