1.5.3 Study Design Rationale

This Phase IIb study is a randomised, double-blind, placebo-controlled study of 365 days duration (plus screening and safety follow-up) that will be conducted to assess the efficacy and safety of monotherapy SC KY1005 in approximately 350 adult patients with moderate-to-severe AD. Sites will be selected globally to participate in this study. A parallel group design will be employed due to the testing of up to 4 different dose regimens versus Placebo. This is considered appropriate for a study of this type (EMEA/CHMP/SWP/28367/07 [Rev. 1] and ICH E4).

The study design, including the washout period and the use of Placebo, is in keeping with other trials in moderate-to-severe AD. The study is designed to assess monotherapy KY1005 in patients with limited treatment options. All patients therefore must have either had an inadequate response to topical therapies or be individuals for whom such topical treatment is inadvisable. It is recognised, based on prior studies in AD with a similar design [Thaçi The Lancet 2016], that the dropout rate can be relatively high (~20%) and this has been factored into the anticipated numbers of patients that will be recruited.

Although the study represents the initial clinical evaluation of SC KY1005, the enrolment of up to 350 patients in a Phase IIb study is considered to be acceptable due to the available clinical data for IV KY1005 in which no KY1005-specific risks have been identified. Furthermore, the non-clinical and clinical data for SC KY1005 have identified no KY1005-specific risks or local toxicity at the injection sites at clinically relevant doses.

The primary objective of this study will be to compare the dose response of 4 different dose regimens of KY1005 in patients with AD versus Placebo to Day 113 (Week 16). As part of the study design, patients initially enrolled at Baseline into the Placebo, 62.5 mg,125 mg and 250 mg KY1005 treatment arms who do **not** achieve ≥ EASI 75 or IGA 0/1 at Day 169 (Week 24) will have the opportunity to be to receive KY1005 from Day 169 (Week 24) by enrolling in an LTE study. This will enable all enrolled patients to have an opportunity to receive treatment at doses expected to elicit a meaningful clinical response (based on what was observed in the Phase 2a KY1005-CT02 study).

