3.6 Randomisation

The Investigator must follow the study randomisation procedures when assigning patients to treatment within the study.

The patient randomisation list will be generated by PPD using Statistical Analysis System (SAS®).

All patients who have completed all Screening assessments and are confirmed as eligible by the Investigator will be randomised to treatment at Baseline. In cases where screen failure occurs due to a laboratory abnormality and is due to reasons expected to change at re-screening and based upon the Investigator's clinical judgment, the patient may be re-screened one time for this study following notification to the Sponsor. Randomisation may be performed up to 24 hours prior to the first administration of KY1005 if all inclusion/exclusion criteria have been satisfied. Each of the 5 treatment regimens (see Table 5-1) will comprise approximately 70 patients (based on 30% drop out rate to Day 169 [Week 24], it is assumed that 49 patients will complete the study) who will be allocated to treatment with KY1005 or Placebo in an equal (1:1:1:1) ratio.

Patients will be centrally randomised. Once confirmed as eligible for the study, patients will be allocated a randomisation number using an IRT system, corresponding to the next available randomised treatment, in a consecutive order starting with the lowest number.

The randomisation will be stratified by disease severity (moderate/severe) and region.

Further randomisation will occur at Day 169 (Week 24) in those patients who achieve ≥ EASI 75 or who attain IGA 0/1. Patients will be randomised in a 3:1 ratio to either enter a withdrawal cohort (receiving Placebo Q4W) or to remain on their pre-Week 24 dose/interval. This Day 169 (Week 24) randomisation will be stratified by IGA response (IGA 0/1 or IGA 2, 3, 4).

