A table, figure, listing is to be generated for any required item even where no data is available or reported. This will ensure the health authorities that the tables, figures, listings and narratives are accounted for. This table, figure or listing will state: “No Data Reported”.

All other statistical analyses performed in part 1 will be performed using a two-sided hypothesis test at the overall 5% level of significance.

P-values will be rounded to four decimal places. If a rounded P-value is less than 0.0001 it will be reported as “<0.0001.”

Unless otherwise specified, baseline will be defined as the last non-missing evaluation prior to study drug administration.

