### 4.1. Sample Size

[figure not shown]
A sample size of 350 patients (70 patients / group) in the target population, (adult with moderate-to-severe AD who have a documented history, within 6 months prior to Baseline, of either inadequate response to topical treatments or inadvisability of topical treatments), randomised 1:1:1:1 to four KY1005 groups or matching Placebo group is estimated to provide at least [REDACTED] power to detect a pairwise difference in means between each KY1005 and Placebo with respect to the percentage change in EASI from Baseline to Day 113 (Week 16), based on a 2-sided 2-sample equal-variance t-test.

[REDACTED]

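### Does the stated 84% power for each KY1005 dose fail once hierarchical testing and dropout are taken into account?

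*Protocol*

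**What the plan says.** The sample size paragraph of the Protocol Synopsis starts from "A sample size of 350 patients (70 patients / treatment arm) in the target population", allocated equally to four KY1005 regimens and placebo. It states that this "is estimated to provide at least 84% power to detect a pairwise difference in means between each KY1005 and Placebo", for percentage change in EASI from Baseline to Day 113, "based on a 2-sided 2-sample equal-variance t-test". SAP Section 4.1 repeats the sentence with the power value blacked out: "is estimated to provide at least [REDACTED] power to detect a pairwise difference in means between each KY1005 and Placebo". The difference and SD behind the figure are not visible in either document (Protocol Section 10.1 and SAP Section 4.1).

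On multiplicity, the Efficacy Analyses part of the Synopsis says that for the primary endpoint "the overall type I error rate will be controlled using a hierarchical testing procedure across the four dose regimens against placebo". The text under the Multiplicity control heading of the SAP is missing from the public copy, so the order of the doses and the gating rule cannot be read. SAP Section 4 sets a "two-sided hypothesis test at the overall 5% level of significance".

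On dropout, Protocol Section 1.5.3 draws on earlier trials of similar design and says that "the dropout rate can be relatively high (~20%) and this has been factored into the anticipated numbers of patients". Section 3.6 describes the 70 per arm as "based on 30% drop out rate to Day 169 [Week 24], it is assumed that 49 patients will complete the study". The full analysis set is all randomised patients (Protocol Section 10.3.1, SAP Section 4.3.2), and SAP Section 8.1 provides multiple imputation for missing values.

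**The concern.** The 84% comes from one two-sample t-test. In a hierarchy, a dose can be claimed only if every dose ahead of it has succeeded, so the chance of a claim for the second to fourth dose is a joint probability and cannot exceed the pairwise power. A reader who takes 84% as the chance of confirming each dose would be too optimistic, and might later read a blocked step as absence of effect. That matters in a trial whose purpose is to describe response over four regimens.

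The two dropout figures add to the doubt. If 84% assumes 70 informative patients per arm, losing 20% or 30% of them would lower it. The protocol does not visibly say which rate, if either, the 70 per arm already contains.

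**Working it through.** **Inputs.** Power of at least 84%, 70 per arm and a two-sided t-test (Protocol Synopsis). Alpha 0.05 two-sided is an assumption taken from SAP Section 4, because the alpha of the power calculation itself is not visible. Dropout of about 20% (Protocol 1.5.3) and 30% to Day 169 (Protocol 3.6).

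**1. Can 84% be reproduced?** Not directly, because the difference and SD are not visible. It can be inverted. With standardised effect d, power = P(T > t), where T is noncentral t with 2n − 2 degrees of freedom and noncentrality d√(n/2), and t is the 97.5% point of the central t. At n = 70, t = 1.977. Setting power to 84% gives:

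| Patients per arm behind the 84% | Implied d |
|---|---|
| 70 (no dropout) | 0.503 |
| 56 (20% dropout) | 0.563 |
| 49 (30% dropout) | 0.603 |

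Round planning effects fit both ends: d = 0.50 at n = 70 gives 83.6%, and d = 0.60 at n = 49 gives 83.7% (84.1% and 84.4% by the normal approximation). The visible text cannot separate these readings.

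**2. Dropout.** 49/0.70 = 70 and 56/0.80 = 70. The 70 per arm is therefore exactly what inflation for either rate would produce.
- If 84% was computed on 70 informative patients and dropouts contribute nothing, power falls to 75.1% at n = 56 and 69.3% at n = 49. The first comparison would fall as much as the others.
- If 84% was computed on 49 completers, power with all 70 informative is 94.3%. On 56 completers it is 91.1%. Both satisfy a claim of at least 84%.

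The lower pair is a pessimistic bound. The 30% runs to Day 169 while the primary endpoint is at Day 113, and all randomised patients are analysed with missing values imputed.

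**3. Hierarchy.** Simulation with 400,000 runs, a shared placebo arm, pairwise t-tests at two-sided 0.05 and a fixed sequence. The entries are the probability that the given step and all earlier steps succeed.

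| Assumed d, in test order | n per arm | Step 1 | Step 2 | Step 3 | Step 4 |
|---|---|---|---|---|---|
| 0.503 in all four | 70 | 84% | 74% | 68% | 62% |
| 0.603 in all four | 70 | 94% | 90% | 87% | 84% |
| 0.77, 0.77, 0.65, 0.503 | 70 | 99% | 99% | 96% | 82% |
| 0.51, 0.51, 0.76, 0.503 | 70 | 85% | 76% | 76% | 69% |

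Pooling the variance over all five arms moves these by at most about one point.

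The last row borrows from Phase 2a (Protocol Table 1-1). The SDs back-calculated from the confidence intervals are 40.3, 39.3 and 40.9, mean 40.2. The high dose gives (69.97 − 49.37)/40.2 = 20.6/40.2 = 0.51, and the low dose gives (80.12 − 49.37)/40.2 = 30.75/40.2 = 0.76. Neither the use of these effects for planning nor a highest-dose-first order is stated in the documents.

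In every row, the stand-alone power of each comparison is at least 84%. Only the chance of passing the gate varies, and it depends on effects and an order that the public copy does not show.

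**The case for a change.** The best case for acting is that the fix costs only wording and the shortfall could be real. Phase 2a found no meaningful difference between the two active arms, and the top regimen here uses the same doses as the Phase 2a high-dose arm, whose effect was about 0.51. If testing starts from the top dose, the gate could already bite at the second step (76%) and leave the fourth at 69%. A dose with a true effect would then go unconfirmed about 24 to 31% of the time, partly because of doses ahead of it in the sequence. The two dropout figures also stand in unredacted text and are not reconciled there.

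Part of this stands. The 84% is a per-comparison figure, the chance of a formal claim for a later dose is usually lower, and one sentence on the dropout basis would help a reader. The stronger reading does not stand. The Synopsis sentence makes no claim about the sequence, so nothing in it is contradicted. The two dropout figures are not the same quantity: one is a rate seen in earlier trials, the other an assumption to Day 169 in this one. A replacement series such as 84, 74, 68 and 62% would put assumed inputs into the protocol in place of the sponsor's own. The feared misreading is also limited in practice: each regimen is compared with placebo, the SAP presents 95% confidence intervals, and the aim is to characterise dose response.

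**Conclusion.** No change is needed. The 84% is marginal power for one dose against placebo, is worded that way, and is not shown to be wrong. Hierarchical testing does not alter it. It lowers the chance of a formal claim for later doses, by anything from about 2 points at the fourth test (graded effects) to about 22 points (84% to 62%, equal effects at exactly 84%). Dropout is not shown to have been left out: the protocol says it was considered, and 70 is exactly the inflated number under either rate.

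This rests on two-sided alpha of 0.05, a fixed sequence, and planning inputs and a test order that are not visible in the public copy. Labelling the figure as marginal and naming the dropout rate behind the 70 per arm would be a courtesy to readers. It would change no test, estimate, sample size or conclusion.

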PROTOCOL SYNOPSIS

Protocol identifier:	KY1005-CT05 (DRI17366)
Study title:	A Phase IIb, Randomised, Double-blind, Placebo-controlled, Parallel Group, Multicentre Dose Ranging Study of a Subcutaneous Anti-OX40L Monoclonal Antibody (KY1005) in Moderate to Severe Atopic Dermatitis Brief title: Study Testing Response Effect of KY1005 Against Moderate to Severe Atopic Dermatitis (STREAM-AD)
Protocol version:	8.0
Sponsor:	Kymab Ltd, a Sanofi Company
Development Phase:	2b
Study type:	Interventional
Indication:	Atopic dermatitis (AD)
Study sites:	Sites will be selected globally to participate in this study.
Study rationale and purpose:	The aim of this study is to characterise the efficacy (including dose/exposure response) and safety of KY1005 across a range of doses/exposures for a maximum duration of 52 weeks in adult patients with moderate-to-severe AD who have had an inadequate response to topical therapies or where topical therapies are not advised. In addition, the durability of response and pharmacokinetics (PK) following withdrawal from the Investigational Medicinal Product (IMP) from Day 169 (Week 24) will be characterised. KY1005 is a human anti-OX40 ligand (OX40L) immunoglobulin G (IgG) 4 monoclonal antibody (mAb) that, via blockade of the OX40/OX40L pathway, is expected to suppress T helper (Th) cell Th2-driven inflammation, as well as potentially modulating Th1, Th17 and Th22 responses. Atopic dermatitis is a chronic/relapsing inflammatory skin disease, characterised by intense pruritus and recurrent eczematous lesions, driven by epidermal barrier dysfunction and cluster of differentiation (CD) 4+ driven inflammation which is dominated by Th2 cytokines.
Primary objective:	To characterise the efficacy (including dose/exposure-response) across a range of KY1005 exposures compared to Placebo on the signs of AD using the Eczema Area and Severity Index (EASI) in those patients with a documented history, within 6 months prior to Baseline, of either inadequate response to topical treatments or inadvisability of topical treatments. Dose response of 4 different dose regimens of KY1005 in patients with AD versus Placebo will be evaluated. The primary efficacy endpoint will be the percentage change in EASI from Baseline to Day 113 (Week 16).

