1.5.2 Rationale for Dose Selection

A total of 4 dosing groups plus Placebo will be tested in this study. The chosen doses and dosing regimens will allow for thorough assessment of the dose and exposure response relationship. This type of approach has been adopted in previous Phase 2b studies in AD [Thaçi D et al, 2016, Guttman-Yassky E 2020]. Given the challenges of needle burden on compliance in AD the ability to provide less frequent dosing has been an influencing factor on the choice of doses and intervals proposed.

The 250 mg SC Q4W with a 500 mg loading dose, 250 mg SC Q4W, 125 mg SC Q4W and 62.5 mg SC Q4W KY1005 doses will be administered o patients to assess the dose/exposure response across an appropriate exposure range.	
250 mg SC Q4W, 125 mg SC Q4W and 62.5 mg SC Q4W KY1005 doses will be administered	
250 mg SC Q4W, 125 mg SC Q4W and 62.5 mg SC Q4W KY1005 doses will be administered	
250 mg SC Q4W, 125 mg SC Q4W and 62.5 mg SC Q4W KY1005 doses will be administered	
250 mg SC Q4W, 125 mg SC Q4W and 62.5 mg SC Q4W KY1005 doses will be administered	The 250 mg SC O4W with a 500 mg loading dose.
	 
o patients to assess the dose/exposure response across an appropriate exposure range.	
	to patients to assess the dose/exposure response across an appropriate exposure range.

Initial treatment period: Dose and interval justification to Day 169 (Week 24)
The dose and dosing regimen that is expected to be able to maintain similar exposures to those observed in CT02 trial, as well as concentrations in tissues above the targeted range during the 24-week double-blind period is a dose of 250 mg administered Q4W. A broad range of doses will be tested in this dose response study to cover the dose range which will capture the dose response and inform the benefit/risk assessment across these dose levels.
The dose and dosing regimen for the period from Baseline to Day 169 (Week 24) for dosing Group 1 is 250 mg administered Q4W, 28 days following a loading dose of 500 mg at Baseline (). Using this approach, this dose and dose regimen is expected to achieve an earlier steady-state, and a C_{max} , from the first dosing, close to that observed in the CT02 trial.

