10.4.2 Efficacy Analysis

An overall test for the treatment effect of KY1005 will be conducted. Pairwise comparisons of each KY1005 treatment group versus Placebo group will be performed.
For the continuous endpoints
An analysis of covariance (ANCOVA) model will be used. This model includes treatment, randomisation strata (region, disease severity) as fixed effects, and baseline value as a covariate.
Covariate.
A mixed-effect model with repeated measures (MMRM) will be used as a sensitivity analysis for primary and continuous key secondary endpoints. This model includes the factors (fixed effects) for treatment, randomisation strata (region, disease severity), visit, treatment-by-visit interaction, and relevant baseline value. Within the framework of MMRM, the treatment difference will be tested at the pre-specified primary timepoint, Day 113 (Week 16), as well as at the other timepoints by timepoint-specific contrasts from the MMRM model.
For the categorical endpoints
Cochran-Mantel-Haenszel test stratified by randomisation strata (region, disease severity) will be used at the analysis timepoint.

Other sensitivity analysis might be performed and details will be specified in the SAP.

Data will be presented graphically, where applicable, and with summary statistics by visit and by treatment regimen.

[figure not shown]

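### The primary objective includes dose/exposure-response, but no readable efficacy analysis compares active doses or estimates a dose-response curve; a supportive one should be pre-specified or cited.

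*Protocol*

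**What the plan says.** **Objective.** The protocol synopsis gives the primary objective as "To characterise the efficacy (including dose/exposure-response) across a range of KY1005 exposures compared to Placebo on the signs of AD", and continues: "Dose response of 4 different dose regimens of KY1005 in patients with AD versus Placebo will be evaluated". Protocol 2.1.1 and SAP 2.1 repeat the objective. Protocol 1.5.3 describes the primary objective as comparing the dose response of the four regimens with placebo up to Week 16. On the regimens, Protocol 1.5.2 says: "The chosen doses and dosing regimens will allow for thorough assessment of the dose and exposure response relationship".

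**Analysis.** The synopsis paragraph on efficacy analyses has no visible gap. It lists:
- an overall test: "An overall test for the treatment effect of KY1005 will be conducted";
- each regimen against placebo: "the analysis will be comparisons of each of the KY1005 treatment groups with the Placebo group";
- multiplicity: "the overall type I error rate will be controlled using a hierarchical testing procedure across the four dose regimens against placebo";
- an ANCOVA: "This model includes treatment, randomisation strata (region, disease severity) as fixed effects, and baseline value as a covariate", with MMRM as sensitivity analysis and CMH for categorical endpoints.

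Protocol 10.4.2 agrees ("Pairwise comparisons of each KY1005 treatment group versus Placebo group will be performed"), and 10.4.2.1 names ANCOVA for the primary endpoint. Power is stated for pairwise differences only (synopsis; SAP 4.1).

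**Exposure.** Population PK modelling is optional in Protocol 10.4.3 and under a separate plan in SAP 10. SAP 10.4 and 10.5 are marked as not applicable.

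**The concern.** Four tests against placebo show which regimens beat placebo. They do not show how the effect changes from 62.5 to 250 mg or where it flattens, which is the dose-ranging question and an input to Phase 3 planning.

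The reader could take differences between the arm means, but they would be imprecise. With an SD of 40 and 70 per arm, the 95% interval for a difference between two arms is about ±13 points, and a true 5-point difference between two active arms would be detected about 11% of the time. A model over all five arms uses the same data better, provided that its shape is about right.

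**Working it through.** **Inputs.**
- From the documents: 350 patients, 70 per arm, 1:1:1:1:1, two-sided 5%, power of at least 84% per pairwise comparison; 49 completers per arm (Protocol 3.6).
- SD: the sample-size inputs are unreadable, so SD = 40 is assumed. It fits Phase 2a (Protocol Table 1-1), taking SE as half the CI half-width: high dose 15.07/2 × √27 = 39; low dose 15.44/2 × √27 = 40; placebo 16.65/2 × √24 = 41.
- Effects (assumed): 14, 17, 19 and 20 points over placebo for 62.5 mg, 125 mg, 250 mg and loading + 250 mg. The top value is close to the Phase 2a high-dose difference, 69.97 − 49.37 = 20.6.
- Dose axis: 0, 62.5, 125, 250, 250.

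**Step 1: the plan's 84%.** Power = P[T′(138 df, δ√(n/2)) > t(0.975)]. With n = 70, δ = 0.50 gives 83.6%, and exactly 84% needs δ = 0.503. With a difference of 20.6 and SD 40, power is 85.7% at n = 70 and 71% at n = 49. So 84% is plausible for 70 evaluable patients per arm, but the stated inputs do not allow it to be reproduced.

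**Step 2: power to detect an effect.** For a contrast c, the noncentrality is Σcᵢμᵢ / [σ√(Σcᵢ²/n)], with pooled df 5(n − 1).

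| Test | n = 70 | n = 49 |
|---|---|---|
| Pairwise: 62.5 / 125 / 250 / loading | 54 / 71 / 80 / 84% | 41 / 55 / 65 / 69% |
| Overall test as 4-df F | 78% | 60% |
| Overall test as pooled active vs placebo | 90.4% | 77.9% |
| Emax contrast, ED50 guessed at 30 to 150 mg | 90.6 to 92.4% | 78.1 to 81.0% |

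The contrast gains about 0 to 2 points over a pooled overall test at n = 70 (0 to 3 at n = 49), and about 12 to 14 points over the F-test at n = 70. The form of the overall test is not readable.

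**Step 3: less favourable shapes, n = 70.**
- Plateau, all regimens 20 points: pooled test 96%, Emax contrast 89 to 95%.
- Non-monotone, with the low dose best as in Phase 2a, largest effect 0.50 SD: a multiple-contrast test with only monotone candidates has 72%, the pooled test 83%, the F-test 70% and the best single pairwise test 84%. (Simulation, 200,000 runs, loading arm placed at 290 mg.)

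**Step 4: precision.** The pairwise SE is σ√(2/n) = 40√(2/70) = 6.76. For an Emax curve with E0, Emax and ED50 all estimated, the delta-method variance is g′[(n/σ²)ΣJJ′]⁻¹g. With a 20-point effect at 250 mg:

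| SE (reduction from 6.76) | ED50 25 | ED50 62.5 | ED50 150 |
|---|---|---|---|
| 62.5 mg vs placebo | 6.48 (4%) | 6.26 (7%) | 5.82 (14%) |
| 125 mg vs placebo | 5.42 (20%) | 5.64 (17%) | 6.01 (11%) |
| 250 mg vs placebo | 5.73 (15%) | 5.74 (15%) | 5.73 (15%) |
| 250 vs 62.5 mg | 5.81 (14%) | 5.68 (16%) | 5.40 (20%) |

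Part of the gain at 250 mg comes only from entering two arms at that dose: pooling them without any curve already gives 40√(1/70 + 1/140) = 5.86.

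**The case against.** **Redaction.** A reader might infer that the plan has no dose-response analysis. The documents do not support that. Table 3 and the multiplicity text in SAP 8.1, the SAP section on changes to the planned analysis, and Protocol 10.4.2.3 are unreadable here, and Protocol 10.4.2 has gaps. The SAP contents list is weak evidence because it also omits the tipping-point, subgroup and multiplicity subsections of 8.1. An exposure-response model could sit in the separate population PK plan. This stands, and it limits the point to the readable text.

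**Use of dose order.** The hierarchy may run in dose order; its order is not readable. Even so, ordering the tests does not estimate a difference between active doses.

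**Power.** A reader might set 84% for a pairwise test against 92% for a contrast and infer a clear loss of power. That compares different hypotheses and leaves out the planned overall test. If that test is pooled, the gain nearly vanishes, and under a plateau it reverses. This stands.

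**Precision.** Treating ED50 as known (62.5 mg) gives SEs of 3.6 to 5.7, which looks like a much larger gain. ED50 will not be known, so the table in step 4 is the fairer guide.

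**Shape.** Phase 2a gave −80.12 at the low dose and −69.97 at the high dose, and the protocol saw no meaningful difference between them. A rising curve cannot be assumed. This argues for several candidate shapes rather than for no model.

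**Conclusion.** The point holds for the readable plan: its primary objective includes dose/exposure-response, and its stated analyses do not estimate it. The benefit of a remedy is chiefly an estimated curve and a direct 250 versus 62.5 mg difference with intervals. SEs are about 4 to 20% smaller versus placebo and about 14 to 20% smaller between those doses, if SD is 40, 70 per arm are evaluable, the Emax model is correct and both 250 mg Q4W arms share one dose. The percentages do not depend on n; the absolute SEs do.

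A claim that the plan sacrifices substantial power is not supported, because that gain depends on the unreadable form of the overall test and on the true shape. The change is worth making. Confidence that it is missing from the full plan is low because of the redactions.

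**What to change.** Leave the pairwise hierarchy and its type I error control unchanged. In SAP 8.1 and Protocol 10.4.2, add a pre-specified supportive dose-response analysis of Week 16 percentage change in EASI, or cite the section that already contains one. It should state:
- the method: MCP-Mod or model averaging on the ANCOVA-adjusted means;
- the candidate shapes, including a plateau and a non-monotone shape;
- the outputs: the fitted curve and the 250 versus 62.5 mg difference, each with a 95% CI;
- the loading-dose arm: entered on a stated exposure metric, or at 250 mg with a repeat analysis that leaves it out.

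**Cost.** SAP and protocol text and one extra analysis, with no new patients or data. The shapes must be fixed before unblinding, including any by-arm interim results, and the estimates will depend on the model.
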